7.2 Study Visits

All procedures and evaluations must be performed at the study site. No study procedures can be conducted until the subject has provided written informed consent.

7.2.1 Pre-Surgery Screening Visit

The Pre-Surgery Screening Visit may take place up to and including 30 days prior to the date of the surgical procedure. The following information shall be collected during the Pre-Surgery Screening Visit:

- Inclusion/Exclusion Determination
- Written informed consent and written authorization for use and disclosure of PHI
- Demographics (age, gender, ethnicity/race)
- Medical History
- Physical Exam, including height, and body weight
- Oswestry Disability Index (lumbar fusion) (Appendix 5) or Neck Disability Index (cervical fusion) (Appendix 6)
- Visual Analog Scale (both leg and back pain) (Appendix 7)
- Radiological Assessment – at minimum, lateral and anterior/posterior radiographs are required at baseline. Flexion and extension radiographs will also be collected if captured by the investigator. If performed, CT scans will also be collected.

7.2.2 Surgical Procedure Visit

The Surgical Procedure Visit shall occur on the same day as the surgical procedure. The following information shall be collected during the Surgical Procedure Visit:

- Surgical procedure details including the type of fusion performed, spine levels involved, ViBone, and other products used.
- If another product is being used in the interbody space, at least 70% of the total volume should be ViBone.

7.2.3 Follow-Up Visits

Study-related Follow-Up Visits shall occur at 6 months and 12 months (\pm 1 month) after the date of the surgical procedure. The following information shall be collected at each Follow-Up Visit:

- Surgical Complication Assessment
- Oswestry Disability Index (lumbar fusion) or Neck Disability Index (cervical fusion)
- Visual Analog Scale (both leg and back pain)
- Radiological Assessment – at minimum, lateral, anterior/posterior, flexion and extension radiographs are required at each follow-up visit. If performed, CT scans will also be collected.

	DOCUMENT TITLE: A Prospective, Post-Market, Multi-Center Study Evaluating ViBone in Cervical and Lumbar Spine Fusion	DOCUMENT NUMBER: CLP-0001
--	--	-------------------------------------

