Patient Population:	
Included are both male and female patients, 18-80 years of age with spondylosis, spondylolisthesis, degenerative disc disease, or herniated nucleus pulposus affecting 1, 2, or 3 contiguous levels of the spine between C2 and C7 (for cervical patients) or L1 and S1 (for lumbar patients).
 
Patients must be undergoing ACDF or lumbar interbody fusion using ViBone to be eligible for the study.

Outcome Measures:	
Primary:
 
 Incidence of successful fusion measured radiographically by 12 months post-surgery 
Secondary:
 
 Incidence of successful fusion measured radiographically by 6 months post-surgery Oswestry Disability Index (ODI)/Neck Disability Index (NDI) relative to baseline. Visual Analog Scale (VAS) relative to baseline. Incidence of subjects experiencing ViBone-related serious adverse reactions.
Duration:	Subjects will be evaluated via routine follow up visits through 12 months post-surgery.
Centers:	Up to 20 centers in the U.S.

	DOCUMENT TITLE: A Prospective, Post-Market, Multi-Center Study Evaluating ViBone in Cervical and Lumbar Spine Fusion	DOCUMENT NUMBER: CLP-0001
--	---	-------------------------------------

Study contact for discussion of protocol-specific issues:

[name]

Aziyo Biologics, Inc.

[contact]

Email: [contact]

**SAFETY REPORTING CONTACT INFORMATION:
REPORTING OF SAFETY INFORMATION TO SPONSOR**

Aziyo pharmacovigilance designee and contact information for adverse reaction reporting:

[name]

Aziyo Biologics, Inc.

[contact]

Email: [contact]

Table of Contents

1	ABBREVIATIONS	7
2	TRADEMARK STATEMENTS	8
3	INTRODUCTION	8
3.1	Spine Fusion	8
3.2	Viable Bone Allografts	8
3.3	Description of ViBone	8
4	STUDY PURPOSE AND OBJECTIVES	9
4.1	Study Purpose	9
4.2	Objectives	9
5	STUDY DESIGN	9
5.1	Design Summary	9
5.2	Patient Enrollment	9
6	PATIENT SELECTION	10
6.1	Study Population	10
6.2	Eligibility criteria	10
6.2.1	Informed Consent Form	10
6.2.2	Inclusion Criteria	11
6.2.3	Exclusion Criteria	11
7	STUDY PROCEDURES	12
7.1	Schedule of Assessments	12
7.2	Study Visits	13
7.2.1	Pre-Surgery Screening Visit	13
7.2.2	Surgical Procedure Visit	13
7.2.3	Follow-Up Visits	13
7.2.4	Subject Close-Out	14

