7 STUDY PROCEDURES

7.1 Schedule of Assessments

Study assessments are summarized below in Table 1, and are further described in Section 7.2.

Table 1: Schedule of Assessments

	Pre-Surgery Screening Visit	Surgical Procedure Visit	Follow-Up Visits (+/- 1 Month)
Visit Window	Day -30 to 0	Day 0	6 and 12 Months Post Surgery
Inclusion/Exclusion Determination	X		
Informed Consent/PHI Authorization	X		
Baseline Demographics and Basic Patient Information	X		
Surgical Procedure Details		X	
Radiological Assessment (including flexion/extension)	X ^{1,2}		X ³
Oswestry Disability Index (Lumbar Fusion) or Neck Disability Index (Cervical Fusion)	X		X
Visual Analog Scale (Both Leg and Back Pain)	X		X
ViBone-Related Serious Adverse Reactions Assessment			As needed

¹ Baseline radiographs may be up to 12 months prior to the surgical procedure.

	DOCUMENT TITLE: A Prospective, Post-Market, Multi-Center Study Evaluating ViBone in Cervical and Lumbar Spine Fusion	DOCUMENT NUMBER: CLP-0001
--	---	-------------------------------------

² Flexion/extension x-rays are not required at baseline, but will be collected if captured.

³ Flexion/extension x-rays are required at all follow-up visits.

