10 OUTCOME MEASURES

The following outcome measures will be assessed at 6 months and 12 months and compared to published and/or retrospective data for autograft or other similar products:

Study objectives are to detect:

- Fusion rates as determined by radiographic imaging at 6 and 12 months post-surgery.
 - Fusion of the interbody space shall be deemed successful if the following radiographic endpoints are demonstrated on x-ray examination (lateral, anterior/posterior, flexion and extension): Evidence of bridging trabecular bone between the involved motion segments, translational motion <3mm; and angular motion <5°.¹
- Changes in Oswestry Disability Index/Neck Disability Index from baseline, at all available follow-up time-points.
- Changes in Visual Analog Scale (VAS) from baseline, at all available follow-up time-points.

Safety evaluations include:

- Incidence of ViBone-related serious adverse reactions.

	DOCUMENT TITLE: A Prospective, Post-Market, Multi-Center Study Evaluating ViBone in Cervical and Lumbar Spine Fusion	DOCUMENT NUMBER: CLP-0001
--	---	-------------------------------------

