11 SAFETY

11.1 Reporting Serious Adverse Reactions

Adverse Reactions involving a communicable disease and are deemed related to use of ViBone, will be reported to FDA's MedWatch program and details of the event shall be documented on the applicable Serious Adverse Reaction form.² Per FDA 21 CFR 1271.3 (y), an adverse reaction is defined as a noxious and unintended response to any HCT/P for which there is a reasonable possibility that the HCT/P caused the response.

Per FDA 21 CFR 1271.350 adverse reactions involving a communicable disease related to an HCT/P (ViBone) must be investigated and reported to the FDA within 15 calendar days of initial receipt of the information. Adverse reactions are further defined to include the following:

A communicable disease that:

1. **Is fatal** (report if you suspect the death was an outcome of the adverse event);
2. **Is life threatening** (subject at substantial risk of dying at the time of the adverse event, or use or continued use of the device or other medical product might have resulted in the death of the subject);
3. **Results in permanent impairment of body function or permanent damage to body structure** (Report if the adverse event resulted in a substantial disruption of a person's ability to conduct normal life functions, i.e., the adverse event resulted in a significant, persistent or permanent change, impairment, damage or disruption in the subject's body function/structure, physical activities and/or quality of life); or
4. **Necessitates medical or surgical intervention, including hospitalization** (report if hospitalization is the result of an adverse event. Emergency department visits that do not result in admission should be evaluated for one of the other outcomes).

If an adverse reaction involving a communicable disease that is believed to be related to the use of ViBone occurs, a Serious Adverse Reaction form shall be completed. In addition to completing the form, Aziyo must be notified within 24 hours of the Investigator becoming aware of the event. All fields are required in order to provide Aziyo personnel with the required information to evaluate the reaction and complete the required MedWatch report for submission to FDA per the Sponsor's Medical Device Reporting SOP.

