Additional tests, including Human T-lymphotropic virus I/II, may have been performed at the time of screening, and results were found acceptable for transplantation. Any additional test(s) performed can be provided upon request. Donor eligibility determination was made by Aziyo Biologics in compliance with U.S. FDA regulations (21 CFR 1270 and 1271) and American Association of Tissue Banks' (AATB™) Standards. The Medical Director determined final eligibility and acceptability for transplantation after review of donor screening and testing records.

WARNINGS AND PRECAUTIONS

An allograft may not elicit proper response from the recipient (e.g. fusion/union with adjacent tissue). It is possible for a host site to become infected or the allograft may cause an inflammatory response. Current technologies may not preclude the transmission of infectious agents or disease, including hepatitis and HIV. ViBone™ is preserved in 5% dimethyl sulfoxide (DMSO) in a 0.9% sodium chloride solution. Povidone iodine, Dulbecco's phosphate buffered saline, sodium chloride irrigation solution, sodium phosphate, hydrochloric acid and hydrogen peroxide are all used for processing, preservation and storage of the allografts and trace amounts of these solutions may be present in the product.

TRANSPORTATION, STORAGE AND HANDLING

ViBone™ is supplied ready to use and must be stored in its original packaging at -75°C to -85°C (-103°F to -121°F) until prepared for use. It is the responsibility of the transplant facility or clinician to maintain the allograft intended for transplantation in the appropriate recommended storage conditions prior to transplant.

HOW SUPPLIED

ViBone™ bone allograft is supplied frozen and packaged in a polycarbonate jar placed in an outer peel pouch. The inner jar and allograft are sterile. The outer peel pouch is not sterile. Allograft volume is indicated on the package label.

STERILITY CONTROL

ViBone™ allografts have been processed under aseptic conditions to prevent contamination and cross contamination of the product. Destructive microbiological testing per USP <71> Sterility Tests is performed on samples from each lot and must show "No Growth" after a 14-day incubation in growth promoting media.

PRECAUTIONS

Inspect the integrity of the package upon receipt and before use. Do not use ViBone™ under the following conditions:

- The container in which the allograft is stored is damaged or the label has been damaged or defaced.

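### Surgical complications are collected at both follow-up visits but tied to no named outcome, and the one safety outcome has a described capture route only for communicable-disease reactions

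*Combined protocol and SAP*

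**What the plan says.** **Collection.** Section 7.2.3 puts "Surgical Complication Assessment" first among the items to be collected at each follow-up visit. It does not say what counts as a complication, over what period, or whether reoperation or relation to the graft is recorded. In Table 1 (Section 7.1) the only safety row is "ViBone-Related Serious Adverse Reactions Assessment", marked for completion as needed.

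**Outcomes.** The synopsis has one safety item, "Incidence of subjects experiencing ViBone-related serious adverse reactions". Section 4.2 carries the same item, and the safety part of Section 10 consists of it alone: "Incidence of ViBone-related serious adverse reactions". None of the three lists names surgical complications or reoperation.

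**Scope of the safety outcome.** Section 11.1 cites the regulatory definition of an adverse reaction, which covers any harmful, unintended response that the graft may reasonably have caused. It then says "Adverse reactions are further defined to include the following", and all four seriousness criteria that follow sit under a communicable-disease stem. The form is triggered by "a communicable disease that is believed to be related to the use of ViBone occurs, a Serious Adverse Reaction form shall be completed".

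**Analysis.** Section 12 is descriptive. It plans counts and percentages with confidence intervals for surgical outcomes, a term it does not define.

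**Known risks.** The package insert (Appendix 4) warns: "It is possible for a host site to become infected or the allograft may cause an inflammatory response". It also warns that the graft may fail to produce fusion.

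**The concern.** A result of no ViBone-related serious adverse reactions will be read as a statement about how patients fared after the graft. If sites fill in the only form described, on the only trigger described, it is mainly a statement about disease transmission. Complications recorded at 6 and 12 months could stay in the database, because no outcome calls for them.

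Two features raise the stakes. Section 10 says its outcome measures will be compared with published or retrospective data for autograft or similar products, and a narrowly captured numerator is a poor basis for that comparison. Section 3.1 also motivates autograft substitutes by the complications of graft harvest, so a reader will expect this study to report its own complications.

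The broad definition and the narrow trigger stand in the same section, so two sites could classify the same event differently. And if complications are tabulated only at the sponsor's discretion, the choice can be made after the data are seen.

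**Working it through.** The plan states no safety event rate, hypothesis or precision target, so there is no figure to reproduce. The check is a tracing of the text, followed by an illustration of size.

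**Step 1. Which events have a committed route into a reported result?**

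| Event | Named outcome | Described capture |
|---|---|---|
| Communicable disease believed related to ViBone, meeting a seriousness criterion | Safety outcome (Section 10) | Form in Section 11.1 |
| Failure to fuse | Primary outcome (its complement) | Radiographs at 6 and 12 months |
| Inflammatory response attributed to the graft | Only if the broad definition in Section 11.1 governs | No form tied to it |
| Surgical-site infection not judged a ViBone-related communicable disease | None named | Complication assessment, undefined |
| Other surgical complication | None named | Complication assessment, undefined |
| Reoperation | None named | Complication assessment, if it asks |

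The first two rows are secure. The other four depend on how an undefined term is read.

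**Step 2. What would a zero on the safety outcome say?**

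Input: up to 50 subjects per cohort (Section 12.1). The synopsis and Section 16.2 say the cohorts are analysed separately, so 50 is the relevant size.

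Exact two-sided 95% upper limit for 0/n: 1 − 0.025^(1/n).

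For n = 50: 1 − 0.025^(1/50) = 0.0711, or 7.1%.

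That limit applies only to events the capture rule can register. It does not bound the complication rate.

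**Step 3. How many affected subjects could lie outside it?**

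The documents give no complication or reoperation rate, so the rates p below are assumptions. Expected number = 50p. Chance of at least one = 1 − (1 − p)^50.

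| Assumed rate | Expected among 50 | Chance of at least one |
|---|---|---|
| 2% | 1.0 | 63.6% |
| 5% | 2.5 | 92.3% |
| 10% | 5.0 | 99.5% |
| 15% | 7.5 | 99.97% |

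If none of these were a communicable-disease reaction, the safety outcome on the narrow reading would still be 0/50.

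**Step 4. What would the missing table show?**

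With 5 of 50 subjects affected, the estimate is 10% with an exact 95% interval of 3.3% to 21.8%. That is imprecise, but it describes complications, which 0/50 does not.

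**The case against.** There is a fair case against much of this.

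- **Failure to fuse is counted.** A reader might infer that the insert's non-fusion warning goes unreported. It does not: fusion by 12 months is the primary outcome, and disability and pain changes are secondary outcomes. This part of the objection stands fully.
- **Section 12 may already cover complications.** Surgical outcomes could include them. So the documents do not support saying that complication data will be left out of the report. They support saying that the plan does not commit to including them.
- **Section 11.1 does not say that nothing else counts.** It sets a regulatory duty for one class of event, and its general definition is wider. The package insert also asks physicians to report any adverse outcome possibly attributable to the graft. This stands as a reason to call the scope ambiguous. But no study form or analysis is tied to the wider definition, and the insert's duty runs from physician to manufacturer.
- **Table 1 is a summary.** Medical history and physical examination are required by Section 7.2.1 and have no rows of their own either. The missing row is therefore weak evidence by itself; the absence from every outcome list carries the point.
- **This is a descriptive registry with no safety hypothesis.** True, but the request is descriptive too and uses the kind of summary Section 12 already plans. Which subcategories to list is partly a matter of judgement.

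**Conclusion.** The point holds as a gap between what is collected and what is committed to reporting, joined to an unresolved scope for the one safety outcome. Inflammatory response, non-communicable complications and reoperation have no committed route into the safety results.

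A reader might go further and infer that the study can report clean safety whatever complications occur. The documents do not support that. A ViBone-related communicable infection counts on any reading, an inflammatory response could count under the broad definition, and Section 12 leaves room for a complications table.

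The size is illustrative: 0/50 with an upper limit of 7.1% could sit beside 2.5 to 5 expected affected subjects per cohort. This rests on a full cohort of 50, assumed rates of 5% to 10%, and sites following the narrow trigger. The textual gap itself does not depend on those rates. The change should be made, but the primary outcome does not turn on it.

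**What to change.** 1. Add a secondary safety outcome to the synopsis, Section 4.2 and Section 10: for each cohort separately, the number and percentage (95% CI) of treated subjects with any surgical complication through 12 months. List index-level reoperation and surgical-site infection separately, and give the investigator's assessment of relation to ViBone.
2. Define the complication assessment in Section 7.2.3 so that it records what this outcome needs, and add it as a row in Table 1.
3. In Section 12, name this outcome among the surgical outcomes to be tabulated.
4. Reconcile Sections 10 and 11.1 by stating whether a ViBone-related serious adverse reaction, as an outcome, extends beyond communicable disease. Keep the regulatory reporting requirement in Section 11.1 as a separate matter.

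The cost is protocol wording and one extra descriptive table. A few eCRF fields for reoperation, infection and relatedness may also be needed, since the protocol does not show that the current assessment captures them. No visit is added and patient management is unchanged.

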7.2.4 Subject Close-Out

The Subject Close-Out shall be performed for all patients enrolled, as well as if either:

- (1) A subject is assigned a subject ID in the EDC, but does not undergo treatment;
- (2) A subject terminates early from the study for any reason.

7.3 Study Monitoring

Individual study sites may be monitored periodically to assure satisfactory enrollment, data recording, and adherence to the protocol. The frequency of monitoring of a study site may vary depending on its enrollment rate and the quality of data collected. The Investigator and staff are expected to cooperate with the monitor at each site visit and provide all relevant study documentation upon request for review. In addition to regular visits, each site may be monitored by phone and/or fax to keep abreast of subject status and to answer questions.

7.4 Protocol Deviations

This study will be conducted as described in this protocol, except for an emergency situation in which the protection, safety, and well-being of the subject requires immediate intervention, based on the judgment of the Investigator (or a responsible, appropriately trained professional designated by the Investigator). In the event of a significant unforeseen deviation from the protocol (e.g., deviation impacting subject safety, obtaining informed consent prior to conducting study procedures, control of study product), the Investigator or his or her designee must contact Aziyo immediately by telephone. When at all possible, the deviation should also be reviewed/approved by the IRB in accordance with IRB policies.

8 STUDY PRODUCT

8.1 ViBone Formulation and Packaging

The Package Insert contains a full discussion of ViBone formulation and packaging. (Appendix 4).

8.2 Labeling and Storage

The product label contains the elements required by the code of federal regulations (CFR), the American Association of Tissue Banks (AATB) and other local authorities for tissue products.

ViBone is supplied ready to use and must be stored in its original packaging at -75°C to -85°C until prepared for use. It is the responsibility of the transplant facility or clinician to maintain the allograft intended for transplantation in the appropriate recommended storage conditions prior to transplant.

	DOCUMENT TITLE: A Prospective, Post-Market, Multi-Center Study Evaluating ViBone in Cervical and Lumbar Spine Fusion	DOCUMENT NUMBER: CLP-0001
--	---	-------------------------------------

8.3 Study Treatments

8.3.1 Treatment Regimen

ViBone will be implanted at the time of surgery.

8.3.2 Study Duration

Subjects enrolled in the registry will be followed for 12 months.

9 PREMATURE SUBJECT WITHDRAWAL

Participation is voluntary and all subjects have the right to withdraw their participation from the study at any time. Subjects will be withdrawn from the study immediately if any of the following occurs:

- the Investigator determines it is in the best interest of the subject, or
- the subject withdraws informed consent, or
- the subject withdraws authorization to use protected health information.

Aziyo or its designee must be notified promptly when a subject is withdrawn. The Investigator will encourage all subjects who decide to withdraw from the study to complete all evaluations that may be necessary to ensure that the subject is free of untoward effects and to seek appropriate follow-up for any continuing problems. The date the subject is withdrawn from the study and the reason for discontinuation will be recorded in the electronic data capture system. When a subject is withdrawn from the study, regardless of the reason, all evaluations required at the final study visit should be performed.

